6.4 STUDY TREATMENT COMPLIANCE

When participants are dosed at the site, they will receive study treatment directly from the investigator or designee, under medical supervision.

Details on treatment administration (e.g., dose and timing) should be noted in the source documents and on the Study Drug Administration electronic Case Report Form (eCRF). Cases of accidental overdose or medication error, along with any associated adverse events, should be reported as described in [Appendix 3](#).

6.5 DOSE MODIFICATION

Baloxavir marboxil is administered as a single-dose treatment, so no dose modification or treatment discontinuation is possible. Modification of the oseltamivir dose is not permitted; however, participants who received oseltamivir can discontinue treatment if adverse events are considered to be related to oseltamivir.

6.6 CONTINUED ACCESS TO STUDY TREATMENT AFTER THE END OF THE STUDY

Currently, the Sponsor does not have any plans to provide baloxavir marboxil or oseltamivir or any other study treatments to participants who have completed the study. The Sponsor may evaluate whether to continue providing baloxavir marboxil in accordance with the Roche Global Policy on Continued Access to Investigational Medicinal Product, available at the following website:

https://www.roche.com/policy_continued_access_to_investigational_medicines.pdf

6.7 TREATMENT OF OVERDOSE

An overdose is the administration of a drug in a quantity that is higher than the assigned dose. There is no known antidote for treating an overdose. Cases of overdose, along with any associated adverse events, should be reported as described in [Appendix 3](#).

In the event of an overdose, the investigator should take the following steps:

1. Contact the Medical Monitor immediately.
2. Closely monitor the participant for any adverse event or serious adverse event and laboratory abnormalities for a period per the investigator's judgement.
3. Obtain a plasma sample for PK analysis within 1 day from the date of the last dose of study treatment if requested by the Medical Monitor (determined on a case-by-case basis).

6.8 CONCOMITANT THERAPY

Concomitant therapy consists of any medication (e.g., prescription drugs, over-the-counter drugs, vaccines, herbal or homeopathic remedies, nutritional supplements) used by a participant in addition to protocol-mandated treatment from 2 weeks prior to the initiation of study drug to the study completion/discontinuation visit.

All such medications must be reported to the investigator and recorded on the Concomitant Medications eCRF along with the following information:

- Reason for use
- Dates of administration, including start and end dates
- Dosage information, including dose and frequency

The Medical Monitor may be consulted if there are any questions related to concomitant or prior therapy.

6.8.1 Permitted Therapy

Acetaminophen is permitted between Days 1–29 for severe influenza symptoms at a dose appropriate to the weight and age of the child. See Section 6.1.3 for further details.

6.8.2 Cautionary Therapy

Baloxavir marboxil co-administration with dairy products, calcium-fortified beverages, polyvalent cation-containing laxatives, antacids, or oral supplements (e.g., calcium, iron, magnesium, selenium, or zinc) should be avoided.

6.8.3 Herbal Therapies

Concomitant use of herbal therapies (including Chinese traditional medications) during this study is strongly discouraged because their pharmacokinetics, safety profiles, and potential drug–drug interactions are generally unknown.

6.8.4 Prohibited Therapy

The use of the following drugs and over-the-counter drugs will be prohibited from the time of signing the informed consent until completion of study assessments on Day 15 (or until completion of assessments at study withdrawal). The concomitant use of topical skin preparations like a compress is allowed.

- Antipyretics/analgesics other than acetaminophen
- Corticosteroids in oral, injection, or *nasal* formulation

Only systemic (oral, injection, rectal or enema) and nasal formulations will be prohibited. The concomitant use of inhaled corticosteroids is allowed, and any changes in dose and mode of administration should be recorded.

- Immunosuppressive agents
- Antibiotics and antifungals

Unless bacterial or fungal infection is suspected after study drug administration.

- *Other systemic antivirals except for study drugs, including traditional Chinese medicines with antiviral effects*
- Influenza vaccines
- Other investigational drugs

7. DISCONTINUATION OF STUDY TREATMENT AND PARTICIPANT DISCONTINUATION OR WITHDRAWAL

Study and site closure is described in [Appendix 1](#).

7.1 DISCONTINUATION OF STUDY TREATMENT

It may be necessary for a participant to permanently discontinue (definitive discontinuation) study treatment. If study treatment is definitively discontinued, the participant will remain in the study for additional assessments. The primary reason for study treatment discontinuation should be documented on the appropriate eCRF.

Participants must permanently discontinue study treatment if any of the following criteria are met:

- Study termination or site closure
- Participant withdrawal of consent
- Any medical condition that the investigator or Sponsor determines may jeopardize the participant's safety if he or she continues to receive study treatment
- Investigator or Sponsor determination that treatment discontinuation is in the best interest of the participant
- If the participant or any other household members/close contact is diagnosed with the SARS-CoV-2 infection by a healthcare professional/institution, and Chinese public health guidance at the time prevents the participant participating in mandatory study visits the participant will be discontinued from the study, with cessation of clinic and/or home visits. Following discontinuation from the study and if not already assessed that day, an early discontinuation visit should be conducted remotely (e.g., via telephone). Collection of a respiratory sample will not be required (see Section [5.4](#)).

The primary reason for study treatment discontinuation should be documented on the appropriate eCRF.

Participants who discontinue study treatment prematurely will not be replaced. Participants will return to the clinic for a treatment completion or treatment discontinuation visit on Day 29 (± 3 days) (see [Appendix 1](#) for additional details). See the schedule of activities (see Section [1.3](#)) for data to be collected at the time of discontinuation of study treatment and for any further follow-up evaluations that need to be completed

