3. OBJECTIVES, ESTIMANDS, AND ENDPOINTS

This study will evaluate the safety, pharmacokinetics, and efficacy of baloxavir marboxil in Chinese pediatric participants aged 1 to < 12 years with influenza symptoms.

[Table 3](#) presents the primary and secondary objectives for the study expressed with use of the estimand framework in accordance with the International Council for Harmonisation (ICH) E9(R1) statistical principles for clinical trials (U.S. Food and Drug Administration [FDA] 2021). [Table 4](#) presents the remaining objectives and corresponding endpoints.

Table 3 Primary and Secondary Objectives and Corresponding Estimand

| Safety (Primary) Objective | Estimand Definition |
|--|--|
| 
 To describe the safety of a single dose of baloxavir marboxil compared with 5 days of oseltamivir administered BID in Chinese pediatric participants | 
 Population: All participants aged 1 to < 12 years with influenza symptoms who received at least 1 dose of study treatment (see Sections 5.1 and 5.2, respectively) Endpoint: 
 Incidence, severity, and timing of adverse events, serious adverse events, with severity determined according to NCI CTCAE v5 Change from baseline in vital sign measurements Change from baseline in clinical laboratory test results Treatment: 
 Experiment arm: baloxavir marboxil single dose Control arm: oseltamivir 5 days BID Intercurrent events and handling strategies 
 Treatment discontinuation: treatment policy strategy Rescue medication: treatment policy strategy Population-level summary: 
 No formal statistical testing will be conducted. Analyses will be descriptive. Incidence of adverse events, serious adverse events by System Organ Class, by Preferred Term and by worst severity Change from baseline summaries will be presented overall and by treatment with use of descriptive statistics, including means, standard deviations, medians, and ranges for continuous variables |

Table 3 Primary and Secondary Objectives and Corresponding Estimand (cont.)

| Efficacy (Secondary) Objective | Estimand Definition |
|---|--|

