7.3 PARTICIPANTS LOST TO FOLLOW-UP

A participant will be considered lost to follow-up if he or she repeatedly fails to return for scheduled visits and is unable to be contacted by the study site.

The following actions must be taken if a participant fails to return to the clinic for a required study visit:

- The site must attempt to contact the participant and reschedule the missed visit as soon as possible and counsel the participant on the importance of maintaining the assigned visit schedule. If the participant is unable or unwilling to comply with study visits, site personnel should assess reasons the participant is unable or unwilling to return to the clinic, and determine if there are ways to support participant participation.
- Before a participant is deemed lost to follow-up, the investigator or designee must make every effort to regain contact with the participant (where possible, three telephone calls and, if necessary, a certified letter to the participant's last known mailing address or local equivalent methods). These contact attempts should be documented in the participant's medical record.
- Should the participant continue to be unreachable, he or she will be considered lost to follow-up and will be withdrawn from the study.

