8.10.1.2 Samples Collected Post-Randomization

One sample is collected for central laboratory analysis according to the schedule of activities (Section [1.3](#)).

Furthermore, the investigator may at any time collect a sample for local analysis of SARS-CoV-2 if the investigator suspects co-infection. If a participant has a positive SARS-CoV-2 result based on a local analysis, all swabbing will stop and they should be discontinued (see Section [7.1](#)).

Sample collection may be performed by an MN professional.

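### The SARS-CoV-2 rule in Protocol 7.1 ends study participation for a reachable, consenting child when only visits and swabs need to stop, so new non-serious AEs need not be sought through Day 29 (minor, cheap to fix)

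*Protocol*

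**What the plan says.** Protocol 7.1 lists reasons for permanently stopping study treatment. Its general rule is that after stopping treatment "the participant will remain in the study for additional assessments", and it closes with "Participants will return to the clinic for a treatment completion or treatment discontinuation visit on Day 29". The last bullet in the list works differently. It needs two things: a SARS-CoV-2 diagnosis in the child, a household member or a close contact, and public health guidance that prevents mandatory visits. When both hold, "the participant will be discontinued from the study, with cessation of clinic and/or home visits". A remote early discontinuation visit is then held, with the telephone given as the example, and no respiratory sample is required.

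Protocol 8.10.1.2 covers a positive local SARS-CoV-2 test after randomization: "all swabbing will stop and they should be discontinued", with a pointer to 7.1. It does not repeat the guidance condition, and it does not say whether treatment or study is meant. For baloxavir it cannot mean treatment, because Protocol 6.5 says the drug is a single dose, "so no dose modification or treatment discontinuation is possible".

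Four other places matter:

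- **Protocol 8.3.1** asks for all AEs until 28 days after the first dose, but removes any duty to seek AEs or SAEs actively once participation has ended.
- **SAP 4.1.1** includes AE data in the summaries up to the date of study completion or discontinuation.
- **Protocol Appendix 3, A3-5.2** requires SAEs and AESIs to be reported to 28 days, and **Protocol 8.3.3** requires AEs already reported to be followed.
- **Protocol 4.1** and the schedule of activities allow the Day 29 visit to be remote.

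**The concern.** The trigger is neither withdrawal of consent nor loss of contact. It is a diagnosis together with a restriction on visits, and the bullet itself expects the family to be reachable. The restriction justifies stopping visits and swabs. It does not require the child to leave the study.

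Protocol 7.3 makes a useful contrast. A family that stops attending is counted as lost only "if he or she repeatedly fails to return for scheduled visits and is unable to be contacted by the study site". A family that can be telephoned is kept under that section but removed under the SARS-CoV-2 bullet.

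AE incidence is part of the primary endpoint. For a child removed in the first days, most of the 28-day AE period would have no active follow-up, although a telephone call could supply it. For an oseltamivir child who stops treatment early, there is a further cost. The primary safety estimand states "Treatment discontinuation: treatment policy strategy", which needs AE data after stopping.

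**Working it through.** **Step 1: what is lost and what is kept after exit.**

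| Data | Position after the early discontinuation contact |
|---|---|
| New AEs, neither serious nor AESI | Need not be actively sought (Protocol 8.3.1); outside the AE data cut (SAP 4.1.1) |
| SAEs and AESIs | Reporting still required to 28 days (A3-5.2) |
| AEs already reported | Still followed (Protocol 8.3.3) |

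The withdrawal row in the SAP 4.1.1 window table, which allows 14 days after withdrawal, applies to measurements taken at visits. AEs follow the separate data-cut rule in the same section. The exposed part is therefore mainly the first row of the table above.

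**Step 2: reproduce the plan's figure.** Inputs from Protocol 9.1.1: n = 67 baloxavir children and true AE incidence p = 3%. The chance of at least one case is 1 − (1 − p)^67 = 1 − 0.97^67 = 87.0%, which matches the stated 87%. The other entries in Protocol Table 8 also reproduce: 49.0%, 74.2%, 93.5% and 96.8% for 1%, 2%, 4% and 5%.

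**Step 3: let k children leave early.** If a share s of a leaver's AE onsets falls before exit, the chance becomes

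1 − (1 − p)^(67 − k) × (1 − p·s)^k.

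The documents give neither k nor the day of exit nor the timing of AEs. The assumed range is k = 0 to 3, that is 0% to 4.5% of 67. With onsets spread evenly over 28 days, exit on Day 4 gives s = 3/28 and exit on Day 10 gives s = 9/28. As an alternative in which AEs come early, s = 0.8.

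| Children leaving | Assumption | Calculation | Result |
|---|---|---|---|
| 0 | none | 1 − 0.97^67 | 87.0% |
| 1 | Day 4, even onset | 1 − 0.97^66 × (1 − 0.03 × 3/28) | 86.6% |
| 1 | Day 10, even onset | 1 − 0.97^66 × (1 − 0.03 × 9/28) | 86.7% |
| 3 | Day 4, even onset | 1 − 0.97^64 × (1 − 0.03 × 3/28)^3 | 85.9% |
| 3 | Day 10, even onset | 1 − 0.97^64 × (1 − 0.03 × 9/28)^3 | 86.2% |
| 3 | 80% of onsets before exit | 1 − 0.97^64 × (1 − 0.03 × 0.8)^3 | 86.8% |

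The largest fall is 1.1 points. With early AE onset, three leavers cost 0.2 points.

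**Step 4: the single affected child.** Active AE follow-up covers 3 of 28 days for exit on Day 4 and 9 of 28 for exit on Day 10. These are calendar days, not shares of AEs.

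**The case against.** The strongest objection is size. The trial tests no hypothesis and has no formal sample-size calculation, so the change is about one point at most on a descriptive figure. The rule needs guidance that blocks visits, and the documents do not contain that guidance. Entry requires a negative SARS-CoV-2 test and excludes suspected cases and close contacts. All of this stands.

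A second objection is that the 28-day AE period has no stated exception for children who leave, so the loss is partly inferred. This stands in part. The reporting period is unqualified, but 8.3.1 also ends active seeking when participation ends, and SAP 4.1.1 cuts the AE data at discontinuation.

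A third is that Protocol 7.2 already lets the investigator withdraw a participant for safety or administrative reasons and refers to the schedule for further evaluations. That is so, but 7.2 leaves the matter to judgement, whereas the bullet directs exit. The last column of the schedule serves both Day 29 and early termination, so no contact is scheduled after an early termination visit.

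Two stronger readings are tempting and should not be drawn:

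- **A reader might infer that 7.1 flatly contradicts itself.** The same list contains withdrawal of consent and study termination, which also end participation. The bullet states its own consequence and procedure. It is a study-exit exception placed in a treatment-discontinuation list, which is untidy but readable.
- **A reader might infer that the rule breaks the treatment-policy estimand in both arms.** A baloxavir child cannot discontinue treatment, so study exit there is simply missing data. The argument reaches only oseltamivir children who stop early, and the figures above are for baloxavir.

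**Conclusion.** The point holds as a minor improvement. As written, the rule gives up some primary-endpoint data from families who consent and can be telephoned, and nothing in its purpose requires that. The loss is mainly new non-serious, non-AESI events after the early discontinuation contact.

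The numerical effect is 0 to 1.1 percentage points on the 87% figure. It rests on an assumed 0 to 3 leavers among 67 and on assumed exit days and AE timing; the true number may be zero. A reader might go further and infer material harm to the safety summary, or a general loss of serious-event reporting. The documents support neither. The case for change is that the loss is avoidable at very low cost.

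**What to change.** - **Protocol 7.1:** replace study discontinuation in the SARS-CoV-2 bullet with stopping swabs and in-person visits, and oseltamivir if indicated. Unless consent is withdrawn, collect AEs, SAEs and concomitant medications by telephone at the remaining scheduled visits through Day 29. The child then stays inside the SAP 4.1.1 data cut.
- **Protocol 8.10.1.2:** give the same consequence, and say whether the guidance condition in 7.1 applies to a positive local test.
- **Diary:** a child kept in the study would otherwise remain on the diary schedule to Day 15. State that the diary stops when visits stop. If it continues, the SAP first needs a rule for SARS-CoV-2 co-infection in the symptom endpoints, because the efficacy estimand lists only treatment discontinuation and rescue medication as intercurrent events.

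The cost is a protocol amendment, with IRB/EC and health authority approval if it counts as substantial (Appendix 1, A1-1), and a few telephone calls per affected child. COVID-19 events would enter the AE tables. Laboratory, vital-sign, swab and PK data from missed visits are not recovered.

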7.2 PARTICIPANT DISCONTINUATION OR WITHDRAWAL FROM THE STUDY

A participant may withdraw from the study at any time at his or her own request or may be withdrawn at any time at the discretion of the investigator for safety, behavioral, compliance, or administrative reasons.

The primary reason for discontinuation from the study should be documented on the appropriate eCRF. If a participant requests to be withdrawn from the study, this request must be documented in the source documents and signed by the investigator.

At the time of discontinuing from the study, if possible, an early discontinuation visit should be conducted, as shown in the schedule of activities (see Section 1.3). See the schedule of activities for data to be collected at the time of study discontinuation and follow-up and for any further evaluations that need to be completed.

The participant will be permanently discontinued both from the study treatment and from the study at that time.

If a participant withdraws consent from the study, the Sponsor may retain and continue to use any data collected before withdrawal of consent. Samples collected prior to withdrawal may be analyzed, unless the participant specifically requests that the samples be destroyed (as documented in the source documents) or local laws require destruction of the samples. However, if samples have been tested prior to withdrawal, results from those tests will remain as part of the overall research data.

7.3 PARTICIPANTS LOST TO FOLLOW-UP

A participant will be considered lost to follow-up if he or she repeatedly fails to return for scheduled visits and is unable to be contacted by the study site.

The following actions must be taken if a participant fails to return to the clinic for a required study visit:

- The site must attempt to contact the participant and reschedule the missed visit as soon as possible and counsel the participant on the importance of maintaining the assigned visit schedule. If the participant is unable or unwilling to comply with study visits, site personnel should assess reasons the participant is unable or unwilling to return to the clinic, and determine if there are ways to support participant participation.
- Before a participant is deemed lost to follow-up, the investigator or designee must make every effort to regain contact with the participant (where possible, three telephone calls and, if necessary, a certified letter to the participant's last known mailing address or local equivalent methods). These contact attempts should be documented in the participant's medical record.
- Should the participant continue to be unreachable, he or she will be considered lost to follow-up and will be withdrawn from the study.

8. STUDY ASSESSMENTS AND PROCEDURES

Written ICFs and assent forms, where appropriate, for participation in the study must be obtained before performing any study-related procedures (including screening

evaluations). Informed Consent Forms for enrolled individuals and for individuals who are not subsequently enrolled will be maintained at the study site.

Study procedures and their timing are summarized in the schedule of activities (see Section 1.3). Protocol waivers or exemptions are not allowed.

Urgent safety concerns should be discussed with the Sponsor immediately upon occurrence or awareness to determine if the participant should continue or discontinue study treatment.

Adherence to the study design requirements, including those specified in the schedule of activities, is essential and required for study conduct.

All screening evaluations must be completed and reviewed to confirm that potential participants meet all eligibility criteria. The investigator will maintain a detailed record of all participants screened, to document eligibility or record reasons for screening failure, as applicable.

Procedures conducted as part of the participant's routine clinical management (e.g., diagnostic test for influenza and/or SARS-CoV-2) within 24 hours of screening may be utilized for inclusion into the study provided the procedures meet the protocol specified criteria and are performed within the timeframe defined in the schedule of activities.

Medical history, including clinically significant diseases, surgeries, cancer history, and reproductive status in female participants will be recorded at baseline. In addition, all medications used by the participant within 2 weeks prior to initiation of study treatment will be recorded. Demographic data, including age, sex, and parent/caregiver will be recorded. Influenza vaccination history for the 12 months before screening will be recorded, including the type of vaccine (e.g., live, inactivated) and date administered, if known.

Physical examinations will be performed at screening and other specified visits. Limited, symptom-directed physical examinations will be performed at specified post-baseline visits and as clinically indicated. Vital signs, including measurements of respiratory rate, pulse rate, and systolic and diastolic blood pressure, as well as tympanic temperature should be recorded.

At applicable sites, certain study assessments may be performed by a mobile nursing (MN) professional at the participant's home or another suitable location to improve access and convenience for participants participating in the study. The Sponsor will select a health-care company that will be responsible for providing MN services for participating sites (the MN vendor). The MN vendor is responsible for ensuring that all MN professionals are licensed, qualified, and in good standing, as per applicable

regulations, and that appropriate background checks have been performed. If the investigator at a participating site determines that MN services are appropriate for a participant and the participant gives written informed consent to participate in MN visits, the MN network will communicate with the participant and the participant's site. MN visits will be scheduled on specified visit days, to allow for relevant assessments to be performed by the MN professional. The schedule of activities (see Section 1.3) will specify the assessments that may be performed by an MN professional.

